17.5. PHYSICAL EXAMINATION

Newly occurring clinically significant physical examination abnormalities will be captured and summarized as AEs. Physical examination data will be listed only.

Author: Version Number: 3.0

Version Date: 06NOV2019

Template No.: CS_TP_BS016 Revision 5 Reference: CS_WI_BS005

Page 54 of 70

17.6. OTHER SAFETY ASSESSMENTS

- The number and percentage of subjects with serum cortisol level $\leq 5 \mu g/dL$ ($\leq 138 \text{ nmol/L}$) or abnormal ACTH stimulation test (serum cortisol $\leq 16 \mu g/dL$ [$\leq 440 \text{ nmol/L}$]) will be presented
- The number and percentage of subjects discontinuing for HPA axis suppression (adrenal suppression) will be presented
- The number and percntage of subjects discontinued for hypercorticism
- The number and percentage of subjects discontinuing due to abnormal ACTH stimulation test will be presented.

Document:

Author:

Version Number: 3.0

Version Date: 06NOV2019

Template No.: CS_TP_BS016 Revision 5 Reference: CS_WI_BS005

Page 55 of 70

APPENDIX 1. PROGRAMMING CONVENTIONS FOR OUTPUTS

IQVIA OUTPUT CONVENTIONS

The standards below apply for all tables, listings and figures. They provide specifications to guide the statistician or statistical programmer in setting up specifications for programming tables, listings and figures. These standards are used in the absence of customer specific standards.

1. ABBREVIATIONS USED BELOW

ASCII American standard code for information interchange file format

CGM Computer graphics metafile

ODS Output Delivery System

RTF Rich text file format

2. OUTPUT FILE NAMING CONVENTIONS

File names should only consist of uppercase letters, lowercase letters, digits (0 to 9) and underscores. A period should only be used to indicate a separator between the file name and the extension. No spaces, other special characters or punctuation marks are permitted.

As far as possible, output files should be in RTF format, although .DOC files are also permitted.

The program, program log and output file name should reflect the type and number of the statistical output. If this is not possible, then the output name should be at least as descriptive as possible. A prefix can be used to distinguish between a Table, Listing and Figure document ('T' for table, 'L' for listing and 'F' for figure). If there is only 1 digit in the number of the table, listing or figure in the place where 2 digits are possible, a leading zero should be added in the file name to make sorting consistent with the sequence (eg T14_3_01_1.RTF)

4. PAPER SIZE, ORIENTATION AND MARGINS

The size of paper will be Letter for the United States, otherwise A4.

The page orientation should preferably be landscape, but portrait is also permitted.

Author:

Version Number: 3.0

Version Date: 06NOV2019

Template No.: CS_TP_BS016 Revision 5 Reference: CS_WI_BS005

Page 57 of 70

Margins should provide at least 1 inch (2.54 centimeters) of white space all around the page, regardless of the paper size.

The number of columns per page (linesize) should be 134 for Letter.

The number of rows per page (pagesize) should be 51 for Letter.

5. FONTS

The font type 'Courier New' should be used as a default for tables and listings, with a font size of 8. The font color should be black. No bolding, underlining italics or subscripting should be permitted. Try to avoid using superscripts, unless absolutely necessary. Single spacing should be used for all text.

Figures should have a default font of "Times Roman", "Helvetica", or "Courier New".

This can be achieved by using the following options in SAS:

goptions

gunit = pct

cback = white

colors = (black)

hby = 2.4

ftext = "TimesRoman"

htext = 2.5

device = cgmof971

gaccess = gsasfile;

filename gsasfile "....cgm";

6. HEADER INFORMATION

Headers should be defined as follows:

- The header should be placed at the top of the page (same place on each page) regardless of the size or orientation of the table or listing
- The customer name and protocol number should appear in row 1, left-aligned
- The output identification number should appear in row 2, centered
- The output title should start in row 3, centered
- The output population should appear in row 4, centered. The population should be spelled out in full, e.g. Intention-to-Treat in preference to ITT.
- Row 5 should be a continuous row of underscores (' ') (the number of underscores should equal the linesize)

Author: Version Number: 3.0
Version Date: 06NOV2019

Template No.: CS_TP_BS016 Revision 5 Reference: CS_WI_BS005

Page 58 of 70

- Row 6 should be a blank line
- Mixed case should be used for titles
- The output titles should be designed so that they are arranged consistently through all outputs. For example, content (eg Vital Signs) followed by metric (eg Change from Baseline) e.g. Vital Signs Change from Baseline.
- Titles should not contain quotation marks or footnote references
- The column headings should be underlined with a row of underscores (' ')
- Column headings spanning more than one column should be underlined and should be centered
- Column headings containing numbers should be centered
- Column headings should be in sentence case
- In general, the population count should appear in the column header in the form "(N=XXX)"
- As a rule, all columns should have column headings.

7. TABLE AND LISTING OUTPUT CONVENTIONS

General:

- The first row in the body of the table or listing should be blank
- The left hand column should start in column 1. No indenting or centering of the output should occur.
- Rounding should be done with the SAS function ROUND.
- Numbers in tables should be rounded, not truncated.
- Alphanumeric output should be left aligned.
- Numbers should be decimal point aligned.
- Whole numbers should be right aligned.
- Text values should be left aligned.
- The first letter of a text entry should be capitalized
- Listings of adverse events, concomitant medications, medical histories etc. should be sorted in chronological order, with earliest adverse event, medication or history coming first.
- The study drug should appear first in tables with treatments as columns
- In general, only present totals (across treatment groups) at baseline/randomization, and do not present them post randomization, unless the customer specifically requests it.
- If possible, include 100% frequencies in the table shell, so that it is clear what the denominator is for percentage calculations.
- All listing outputs should be sorted (preferably by Treatment, Site Number and Subject Number).
- Do not use superscripts and subscripts
- Exponentiation will be expressed using a double asterisk, i.e., mm3 will be written as mm**3.

Author:

Version Number: 3.0

Version Date: 06NOV2019

Template No.: CS_TP_BS016 Revision 5 Reference: CS_WI_BS005

Page 59 of 70

- All variables that are output in the CRF (which have data present) should appear in the listings, along with all derived data appearing in the corresponding tables
- The width of the entire output should match the linesize

Univariate Statistics:

- Statistics should be presented in the same order across tables (i.e., n, Mean, SD, Median, Minimum, Maximum)
- Table statistics should line up under the N part of the (N=XXX) in the table header. All decimal points should line up. If the minimum and maximum are output on one line as Minimum, Maximum then the comma should line up with the decimal point.
- If the original data has N decimal places, then the summary statistics should have the following decimal places: Minimum and maximum: N

Mean, median and CV%: N + 1

SD: N+2

Frequencies and percentages (n and %):

• Percent values should be reported inside parentheses, with one space between the count and the left parenthesis of the percentage. Parentheses should be justified to accept a maximum of 100.0 as a value and padded with blank space if the percent is less than 100.0. An example is given below:

77 (100.0%)

50 (64.9%)

0(0.0%)

• Percentages will be reported to one decimal place, except percents <100.0% but >99.9% will be presented as '>99.9%' (e.g., 99.99% is presented as >99.9%); and percents < 0.1% will be presented as '<0.1%' (e.g., 0.08% is presented as <0.1%). Rounding will be applied after the <0.1% and >99.9% rule.

Eg (<0.1%)

(6.8%)

(>99.9%)

Percentages may be reported to 0 decimal places as appropriate (for example, where the denominator is relatively small).

• Where counts are zero, percentages of 0.0% should appear in the output.

Confidence Intervals:

• As a rule confidence intervals are output to one place more than the raw data, and standard deviations and standard errors to two places more than the raw data

Author:

Version Number: 3.0

Version Date: 06NOV2019

Template No.: CS_TP_BS016 Revision 5 Reference: CS_WI_BS005

Page 60 of 70

- Confidence intervals should be justified so that parentheses displayed on consecutive lines of a table "line up".
- Boundary values of confidence intervals should be separated by a comma.
- Boundary values should be padded as necessary to accept negative values and to allow alignment of the decimal place.
- An example is given below:

(-0.12, -0.10)

(9.54, 12.91)

P-values:

• P-values should be reported to three decimal places, except values <1.000 but >0.999 will be presented as '>0.999' (e.g., 0.9998 is presented as >0.999); and values <0.001 will be presented as '<0.001' (e.g., 0.0009 is presented as <0.001). Rounding will be applied after the <0.001 and >0.999 rule

Ratios:

• Ratios should be reported to one more decimal place than the original data.

Spacing:

• There must be a minimum of 1 blank space between columns (preferably 2)

Denominators:

- If a different count other than the population count is used for a denominator (within the table) to calculate percentages, there should be a row in the table that identifies that number "n".
- Alternatively, a footnote should be included in each table with percentages to indicate the denominator for percentages.

Missing values

- A "0" should be used to indicate a zero frequency.
- A blank will be used to indicate missing data in an end-of-text table or subject listing.

8. FIGURE OUTPUT CONVENTIONS

- Figures should be provided in RTF files using the SAS Output Delivery System (ODS), as Computer Graphics Metafile (CGM) formatted graphical output generated by SAS.
- The CGM file itself should contain the title or footer.

Author:

Version Number: 3.0

Version Date: 06NOV2019

Template No.: CS_TP_BS016 Revision 5 Reference: CS_WI_BS005

Page 61 of 70

- The image should be clear and of high quality when viewed in the Word document, and when printed.
- In general, boxes around the figures should be used.

9. FOOTNOTE INFORMATION

Footers should be defined as follows:

- A continuous line of underscores ('_') will follow the body of the table or listing prior to any footnotes at the bottom of the page
- Table footnotes should be defined using compute statements in the proc report, and should appear directly after the body of the table
- The program path and name and version number (if applicable) should appear as the last footnote at the bottom of the page
- The date/time stamp should also appear in the last footnote at the bottom of the page right aligned
- Footnotes should be left-aligned.
- Footnotes should be in sentence case.
- Only "typewriter" symbols are permitted eg "*", "\$", "#", "@", "&" and "+".
- The choice of footnote symbols should be consistent. E.g. if you have the footnote "# indicates last observation carried forward" for one table, the same symbol and footnote should indicate LOCF for all tables.
- The page identification in the format Page X of Y (where Y is the total number of pages for the output) should appear in the first header, right aligned

Ordering of footnotes should be as follows:

- 1.) Source data listing reference, if necessary
- 2.) Abbreviations and definitions
- 3.) Formulae
- 4.) P-value significance footnote
- 5.) Symbols
- 6.) Specific notes
- Common notes from table to table should appear in the same order.
- The symbols should appear in the same order as what they are defined in the table or listing, from left to right.

10. PROGRAMMING INSTRUCTIONS

Document:

Author:

Version Number: 3.0

Version Date: 06NOV2019

Template No.: CS_TP_BS016 Revision 5 Reference: CS_WI_BS005

Programming instructions must appear in blue font at the end of each table or listing shell. Programming instructions, where necessary, should follow the table or listing shells in blue font, beginning with the words "Programming Note" followed by a colon. These include notes on the output, reminders of how to handle missing values, repeat shells for similar tables etc.

DATES & TIMES

Depending on data available, dates and times will take the form yyyy-mm-ddThh:mm:ss.

SPELLING FORMAT

English US will be used.

PRESENTATION OF DOSING GROUPS

For outputs, dosing groups will be represented as follows and in that order:

Treatment Group	For Tables and Graphs	For Listings (include if different to tables)
		ŕ
APT-1011 3.0 mg BID	APT-1011 3 mg BID	3 mg BID
APT-1011 3.0 mg HS	APT-1011 3 mg HS	3 mg HS
APT-1011 1.5 mg BID	APT-1011 1.5 mg BID	1.5 mg BID
APT-1011 1.5 mg HS	APT-1011 1.5 mg HS	1.5 mg HS
Placebo	Placebo	Placebo
Non-Responders at Week	Single-Blind APT-1011 3 mg BID	Randomized Treatment Group with *
12		concatenated for relevant data
APT-1011 3.0 mg BID	All APT-1011 3 mg BID (with footnotes	Not for use in listings.
and Non-Responders at	explaining this)	
Week 12 (for Safety		
Outputs)		

Author:

Version Number: 3.0

Version Date: 06NOV2019

Template No.: CS_TP_BS016 Revision 5 Reference: CS_WI_BS005

Page 63 of 70

Treatment Group	For Tables and Graphs	For Listings (include if different to tables)
Not Randomized	N/A	Not Randomized

PRESENTATION OF VISITS

For outputs, visits will be represented as follows and in that order:

Long Name (default)	Short Name For Use in Outputs
Visit 1 (Screening)	Screening
Derived Baseline per Parameter	Baseline (for tables only)
Visit 2 (4-week Baseline Symptom Assessment)	Visit 2
Visit 3	Rand.
Visit 4 (Week 4)	Week 4
Visit 5 (Week 8)	Week 8
Visit 6 (Week 12)	Week 12
Visit 7 (Week 14)	Week 14
Visit 8 (Week 18)	Week 18
Visit 9 (Week 22)	Week 22
Visit 10 (Week 26)	Week 26
Visit 11 (Week 28)	Week 28
Visit 12 (Week 36)	Week 36
Visit 13 (Week 44)	Week 44

Author:

Version Number: 3.0

Version Date: 06NOV2019

Template No.: CS_TP_BS016 Revision 5 Reference: CS_WI_BS005

Page 64 of 70

Long Name (default)	Short Name For Use in Outputs
Visit 14 (Week 52)	Week 52
Unscheduled	Unsch
End of Treatment	ЕОТ

LISTINGS

All listings will be ordered by the following (unless otherwise indicated in the template):

- randomized dosing group (or treatment received if it's a safety output), first by active dose [by descending dose
 group] and then placebo
- center-subject ID,
- date (where applicable),
- For listings where non-randomized subjects are included, these will appear in a category after the randomized dosing groups labeled 'Not Randomized'.
- For visits or safety data where the data were captured for non-responders at Week 12 after they had received single-blind APT-1011 3mg BID in Part 2, the visit or the event will be annotated with a * (e.g. Week 28*) for that record with a footnote explaining that * denotes information after the subject received single-blind (to the subject) APT-1011 3 mg BID in Part 2.

APPENDIX 2. Partial Date Conventions

Imputed dates will NOT be presented in the listings.

ALGORITHM FOR TREATMENT EMERGENCE OF ADVERSE EVENTS:

START DATE	STOP DATE	ACTION
Known	Known, Partial or Missing	If start date < study drug start date, then not TEAE If start date >= study drug start date, then TEAE

Author:

Version Number: 3.0

Version Date: 06NOV2019

Template No.: CS_TP_BS016 Revision 5 Reference: CS_WI_BS005

Page 65 of 70

START DATE	STOP DATE	ACTION
Partial, but known components show that it cannot be on or after study drug start date	Known, Partial or Missing	Not TEAE
Partial, could be on or after study med start date	Known	If stop date < study drug start date, then not TEAE If stop date >= study drug start date, then TEAE
	Partial	Impute stop date as latest possible date (i.e. last day of month if day unknown or 31st December if day and month are unknown), then: If imputed stop date < study drug start date, then not TEAE If imputed stop date >= study drug start date, then TEAE
	Missing	Assumed TEAE
Missing	Known	If stop date < study drug start date, then not TEAE If stop date >= study drug start date, then TEAE
	Partial	Impute stop date as latest possible date (i.e. last day of month if day unknown or 31st December if day and month are unknown), then: If imputed stop date < study drug start date, then not TEAE If imputed stop date >= study drug start date, then TEAE
	Missing	Assumed TEAE

ALGORITHM FOR ASSIGNMENT OF TREATMENT EMERGENT ADVERSE EVENTS TO STUDY PARTS:

The rules below will be applied to AEs which were defined as TEAEs using the table above.

Author:

Version Number: 3.0

Version Date: 06NOV2019

Template No.: CS_TP_BS016 Revision 5 Reference: CS_WI_BS005

Page 66 of 70

START DATE	STOP DATE	ACTION
Known	Known,	If start date >= Part 2 study drug start date assign to Part 2
	Partial or	Otherwise:
	Missing	assign to Part 1
Partial	Known	If stop date < Part 2 study drug start date assign to Part 1
		Otherwise:
		If known components of start date are such that the start date
		is definitely >= Part 2 study drug start date, assign to Part 2
		or if known components of start date are such that the start
		date is definitely < Part 2 study drug start date, assign to Part
		1.
		Or if known components of start date are such that the start
		date might be >= Part 2 study drug start date, assign to Part 1
		and Part 2
	Partial	Impute stop date as latest possible date (i.e. last day of month
		if day unknown or 31st December if day and month are
		unknown), then:
		If imputed stop date < Part 2 study drug start date assign to
		Part 1.
		Otherwise:
		If known components of start date are such that the start date
		is definitely >= Part 2 study drug start date, assign to Part 2
		Or if known components of start date are such that the start
		date is definitely < Part 2 study drug start date, assign to Part
		1.
		Or if known components of start date are such that the start
		date might be >= Part 2 study drug start date, assign to Part 1
		and Part 2
	Missing	If known components of start date are such that the start date
		is definitely >= Part 2 study drug start date, assign to Part 2

Author: Version Number:

Version Date: 06NOV2019

3.0

Template No.: CS_TP_BS016 Revision 5 Reference: CS_WI_BS005

Page 67 of 70

START DATE	STOP DATE	ACTION
		Or if known components of start date are such that the start date is definitely < Part 2 study drug start date, assign to Part 1. Or if known components of start date are such that the start date might be >= Part 2 study drug start date, assign to Part 1 and Part 2
Missing	Known	If stop date < Part 2 study drug start date assign to Part 1 and Part 2
	Partial	Impute stop date as latest possible date (i.e. last day of month if day unknown or 31st December if day and month are unknown), then: If imputed stop date < Part 2 study drug start date assign to Part 1 Otherwise: assign to Part 1 and Part 2
	Missing	Assign to Part 1 and Part 2

ALGORITHM FOR PRIOR / CONCOMITANT MEDICATIONS:

START DATE	STOP DATE	ACTION
Known	Known	If stop date < study drug start date, assign as prior
		If stop date >= study drug start date and start date <= end of treatment,
		assign as concomitant
		If stop date >= study drug start date and start date > end of treatment, assign
		as post study

Author:

Version Number: 3.0

Version Date: 06NOV2019

Template No.: CS_TP_BS016 Revision 5 Reference: CS_WI_BS005

Page 68 of 70

START DATE	STOP DATE	ACTION
	Partial	Impute stop date as latest possible date (i.e. last day of month if day unknown or 31st December if day and month are unknown), then: If stop date < study drug start date, assign as prior If stop date >= study drug start date and start date <= end of treatment,
		assign as concomitant If stop date >= study drug start date and start date > end of treatment, assign as post treatment
	Missing	If stop date is missing could never be assumed a prior medication
		If start date <= end of treatment, assign as concomitant
		If start date > end of treatment, assign as post treatment
Partial	Known	Impute start date as earliest possible date (i.e. first day of month if day
		unknown or 1st January if day and month are unknown), then:
		If stop date < study drug start date, assign as prior
		If stop date >= study drug start date and start date <= end of treatment,
		assign as concomitant
		If stop date >= study drug start date and start date > end of treatment, assign as post treatment
	Partial	-
	Partiai	Impute start date as earliest possible date (i.e. first day of month if day unknown or 1st January if day and month are unknown) and impute stop
		date as latest possible date (i.e. last day of month if day unknown or 31st
		December if day and month are unknown), then:
		If stop date < study drug start date, assign as prior
		If stop date >= study drug start date and start date <= end of treatment,
		assign as concomitant
		If stop date >= study drug start date and start date > end of treatment, assign
		as post treatment

Author:

Version Number: 3.0

Version Date: 06NOV2019

Template No.: CS_TP_BS016 Revision 5 Reference: CS_WI_BS005

Page 69 of 70

START DATE	STOP DATE	ACTION
	Missing	Impute start date as earliest possible date (i.e. first day of month if day
		unknown or 1st January if day and month are unknown), then:
		If stop date is missing could never be assumed a prior medication
		If start date <= end of treatment, assign as concomitant
		If start date > end of treatment, assign as post treatment
Missing	Known	If stop date < study drug start date, assign as prior
		If stop date >= study drugstart date, assign as concomitant
		Cannot be assigned as 'post treatment'
	Partial	Impute stop date as latest possible date (i.e. last day of month if day
		unknown or 31st December if day and month are unknown), then:
		If stop date < study drug start date, assign as prior
		If stop date >= study drug start date, assign as concomitant
		Cannot be assigned as 'post treatment'
	Missing	Assign as concomitant

Author: Version Number: 3.0

Reference: CS_WI_BS005

06NOV2019

Version Date:

Template No.: CS_TP_BS016 Revision 5

Page 70 of 70

Document:

Author:

Version Number: 3.0

Version Date: 06NOV2019

Template No.: CS_TP_BS016 Revision 5 Reference: CS_WI_BS005

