17.1. ADVERSE EVENTS

Adverse Events (AEs) will be coded using the MedDRA coding dictionary, Version 21.0.

Treatment emergent AEs (TEAEs) are defined as AEs that started or worsened in severity on or after the first dose of study drug. In section 5.0 of the protocol it states: 'the term study drug is used to refer to any blinded medication administered (i.e., any dosage of APT-1011 or placebo)'.

For further defining TEAEs below, study drug will also include single-blind (to subject) APT-1011 3.0 mg BID which histologic non-responders at Week 12 receive in Part 2.

TEAEs will be defined for each of the following periods:

- Part 1 of the study
- Part 2 of the study (with first dose of study drug being the first dose in Part 2)
- Parts 1 and 2 combined

For Parts 1 and 2 combined, histologic non-responders at Week 12 will be summarized for both their double-blind dosing in Part 1 and their single-blind (to subject) dosing in Part 2.

See Appendix 2 for handling of partial dates for AEs. In the case where it is not possible to define an AE as treatment emergent or not, the AE will be classified by the worst case; i.e. treatment emergent.

An overall summary of number of subjects and number of events within each of the categories described in the sub-

Author:

Version Number: 3.0

Version Date: 06NOV2019

Template No.: CS_TP_BS016 Revision 5 Reference: CS_WI_BS005

Page 49 of 70

section below, will be provided as specified in the templates.

Listings will include TEAEs and Non-TEAEs.

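### SAP Appendix 2 counts an adverse event with no start date in Part 2 even when it ended before Part 2, and has no rule if it ended later

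*SAP*

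**What the plan says.** Appendix 2 of the SAP works in two stages. One table decides whether an adverse event is treatment emergent. A second table allocates it to a study part: "The rules below will be applied to AEs which were defined as TEAEs using the table above".

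In the second table, the whole entry for a missing start date with a known stop date is "If stop date < Part 2 study drug start date assign to Part 1 and Part 2". The entry directly beneath covers a missing start date with a partial stop date. It imputes the stop date as late as possible and then has two branches: "If imputed stop date < Part 2 study drug start date assign to Part 1 Otherwise: assign to Part 1 and Part 2". The entry for a partial start date with a known stop date opens with "If stop date < Part 2 study drug start date assign to Part 1" and goes on to deal with the remaining cases. The partial-start, partial-stop entry applies the same test to the imputed stop date, with the same result.

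SAP 17.1 sets the definition that these rules serve: "Treatment emergent AEs (TEAEs) are defined as AEs that started or worsened in severity on or after the first dose" of study drug. It applies this by period, the second being "Part 2 of the study (with first dose of study drug being the first dose in Part 2").

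Under SAP 17, Part 2 data for Week 12 histologic non-responders appear in a single-blind 3 mg BID group and in a summary of all 3 mg BID exposure in Part 2.

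**The concern.** The row has two faults.

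- **Stop date before Part 2.** The event is allocated to both parts, although it was over before Part 2 treatment began.
- **Stop date in Part 2.** There is no instruction. The event has already been classed as treatment emergent and should appear in the safety outputs, but nothing says in which part.

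This matters because the part determines the dose column for anyone who changes treatment. A Week 12 non-responder who had an event on placebo or on a lower daily dose, and recovered before Part 2, would also be shown with that event under single-blind 3 mg BID. Long-term safety and dose selection are stated secondary objectives, so the by-dose safety tables should follow the SAP's own definition.

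**Working it through.** The plan states no figure on this point, so the check is mainly a comparison of the rows.

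**Step 1. The rows side by side.**

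| Start date | Stop date | Ended before first Part 2 dose | Ended on or after first Part 2 dose |
|---|---|---|---|
| Partial | Known | Part 1 | Part 1, Part 2 or both, by the known parts of the start date |
| Partial | Partial (imputed latest) | Part 1 | As above |
| **Missing** | **Known** | **Part 1 and Part 2** | **No rule** |
| Missing | Partial (imputed latest) | Part 1 | Part 1 and Part 2 |
| Missing | Missing | Both parts; no test possible | Both parts; no test possible |

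A missing start date gives five cases: known stop before, known stop on or after, partial stop before, partial stop on or after, and missing stop. One of the five conflicts with the other rows and one is undefined. Both are in the same row.

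**Step 2. Against the definition in SAP 17.1.** A Part 2 event must start or worsen on or after the first Part 2 dose. An event that stopped before that dose can do neither, whatever its start date. The missing start date therefore leaves no uncertainty about Part 2 in this case, and Part 1 only is the single allocation that fits the definition.

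**Step 3. Against the row beneath.** With a partial stop date, the SAP takes the latest possible date. If even that precedes Part 2, it allocates to Part 1 only. A fully known stop date carries more information than a partial one, so it cannot justify a less certain allocation.

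**Step 4. Who could have an event shown under a dose not yet taken.** Inputs are from protocol 8.1.1: 20 subjects per arm; Week 12 response of 60% for 3 mg BID, 3 mg HS and 1.5 mg BID, 20% for 1.5 mg HS and 10% for placebo.

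Non-responders = 20 × (1 − response rate):

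- 3 mg BID: 20 × 0.40 = 8
- 3 mg HS: 20 × 0.40 = 8
- 1.5 mg BID: 20 × 0.40 = 8
- 1.5 mg HS: 20 × 0.80 = 16
- Placebo: 20 × 0.90 = 18

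Total = 8 + 8 + 8 + 16 + 18 = 58. The 8 from the 3 mg BID arm were already on that dose in Part 1. A repeated event in them falls in the wrong period but not under a wrong dose. That leaves 58 − 8 = 50 subjects, assuming all continue into Part 2. Week 12 responders keep their dose, so a repeated event in them also changes the period only.

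**The case against.** **The trigger is narrow.** Protocol 6.3.1.2 makes onset date a field on the adverse event form and has the monitor check that form for completeness. Only events with a wholly missing start date and a known stop date reach this row. This stands, and it is why the point is minor.

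**The worst-case fallback.** SAP 17.1 has this rule: "In the case where it is not possible to define an AE as treatment emergent or not, the AE will be classified by the worst". The outcome it intends is that such an event counts as treatment emergent. Read period by period, this could place an event that stopped in Part 2 in both parts, which is the sensible result. That reading is open to a programmer, but the sentence concerns treatment emergence and is not a part-assignment rule. It also cannot make a Part 2 event of one that had already ended.

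**Deliberate caution.** In non-responders the extra count can only add events to 3 mg BID, and SAP 3.3 shows the sponsor avoiding a rule that might flatter the highest dose. But three other rows do not take this approach, and the missing branch works the other way, since it could omit an event that occurred on 3 mg BID.

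**Limited use.** SAP 17 plans no statistical comparison of safety data, listings carry all events, and the interim safety outputs under SAP 4.2 cover Part 1 only. All of this is correct and limits the harm.

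**Lost text.** The table runs across pages, and a few words could have been lost in conversion from PDF. The sentence is complete as it stands and the next row kept its second branch, so this is unlikely, but the source file should be checked.

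A reader might also infer more than the documents support:

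- *That resolved events are moved out of Part 1.* They are not. The row keeps them in Part 1 and adds Part 2, so the fault is double counting.
- *That events ending in Part 2 are certainly dropped.* The SAP is silent. Omission is a risk of literal coding, not a stated outcome.
- *That 58 subjects measures the size.* It is a pre-dropout ceiling on entry to the single-blind group, includes 8 already on 3 mg BID, and says nothing about how many records are affected.

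**Conclusion.** The row is wrong as written. It contradicts three other rows of its own table and the SAP 17.1 definition of a Part 2 event, and it leaves one case without a rule. Followed literally, it double counts an event that resolved before Part 2. For at most about 50 of 100 subjects it would charge such an event to a dose not yet taken. That ceiling rests on the protocol 8.1.1 response rates and on every non-responder continuing.

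The number of affected records is unknown, because neither document counts events with a missing start and a known stop date. It is probably small. The primary and other efficacy analyses are not touched. This is a minor correction to a safety-table rule.

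**What to change.** Rewrite the missing-start, known-stop row with the two branches of the row beneath it. A stop date before the first Part 2 dose goes to Part 1 only; any other known stop date goes to both parts. This agrees with the neighbouring rows and with SAP 17.1 and covers every case.

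The cost is one line of SAP text and the matching line of code, with no new data and no change to study conduct. If the by-part safety programs already exist, check which rule they apply, and list any treatment-emergent events with a missing start and a known stop date so that the actual effect is known.
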